1649 Our primary analyses will compare change in ACP documentation between study arms from 1650 baseline to 15 months. Secondary outcomes will include ACP Engagement with respect to 5 1651 ACP Actions (yes/no and a 0-25-point scale) and behavior change scores (average 5-point 1652 Likert scores) from baseline to 1 week, and 3, 6, and 12 months. Variables will be assessed for distributional and outlier values using standard summary statistics. Baseline comparability will 1653 1654 be assessed between groups using unpaired t-tests, Chi-square tests or Fisher's exact tests. 1655 Using t-tests or Chi-squared tests, we will also compare patient's age and self-reported gender 1656 between those who refused versus those who enrolled and differences between arms of those 1657 who withdrew versus those who did not. We will use intention-to-treat analysis using SAS 1658 version 9.4 (SAS Institute Inc.) and STATA 15.0 (College Station, TX). All p-values will be 2-1659 tailed and set at .05 for the primary outcome and Bonferroni adjusted for secondary patient-1660 reported outcomes. In addition, because of differences in ACP engagement among English and Spanish speakers,⁸ and based on preferences of our stakeholders and granting agencies, we 1661 1662 decided, a priori, to analyze our results overall and stratified by English and Spanish language. 1663 To compare outcomes between the two arms longitudinally, we will use mixed effects linear, 1664 Poisson, or negative binomial regression for continuous measures and mixed effects logistic regression for dichotomous measures. The mixed effects models will include fixed effects for the 1665 1666 primary modeling terms of time (baseline and 15 months for ACP documentation and baseline 1667 and 1 week, 3 months, 6 months, and 12 months for ACP Engagement with time modeled using 1668 dummy variables to allow for non-linearity); arm (AD-only versus PREPARE); an interaction 1669 term of study arm and time; and a random effect for subjects. We will adjust for the randomization blocking factors limited vs. adequate literacy,⁹⁸ and any predictor variables that 1670 1671 differ between arms. All models also will also be adjusted for baseline ACP documentation and will include random physician intercepts to account for nesting of patients within physicians. We 1672 1673 will use standardized, clinically meaningful effect sizes (i.e., 0.20-0.49 small, 0.50-0.79 medium,

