and ≥ 0.80 large).⁹⁹ Per stakeholder request, we will conduct post-hoc mixed-effects regression to calculate the percentage of participants who increased their Behavior Change score, Action scores, or both Behavior Change and Action scores from baseline (i.e., estimated slope > 0) by study arm; p-values adjusted to a significance of 0.017.

1678

1679 For moderator analysis, we will test for interactions by adding interaction terms to the group by 1680 time variable for health literacy (limited versus adequate) controlling for prior ACP 1681 documentation and clustering effects by clinician. All other interaction terms are adjusted for 1682 health literacy (randomization blocking variable) prior ACP documentation and clustering effects 1683 by clinician. Additional interaction terms to be added to the group by time variable include 1684 language (i.e., English versus Spanish), control preferences for decision making (i.e., makes 1685 own decisions versus doctor makes decisions), age (i.e., < 65 years versus \geq 65 years of age), 1686 sex/gender (i.e., self-reported man versus woman), race/ethnicity (i.e., white versus non-white), 1687 health status (i.e., good-to-excellent versus fair-to-poor), presence of a potential surrogate (i.e., 1688 yes versus no), internet access at home (i.e., yes versus no), and, for Spanish-speakers, 1689 patient-clinician language (concordance vs. discordance). A p-value for interaction <0.05 is 1690 considered significant. 1691

Missing data for the primary outcome will be assessed. If there is 10% or more of missing data, we will use a mean imputation approach. All available data will be included in mixed-effects models. We will assess whether any research staff member became unblinded during follow-up assessment and conduct sensitivity analysis as needed.

1696

1697 SAMPLE SIZE AND POWER CALCULATIONS

1698 We will measure a full range of ACP behaviors including discussions. However, written advance 1699 directive completion of legal forms is a primary outcome and is the most well-studied.¹⁰⁰ Power

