1700 from longitudinal analyses with repeated measures will be stronger, but to be conservative, we consider power for a single post-intervention time point (e.g., 15 months). A recent meta-1701 1702 analysis of written advance directive documentation studies demonstrated a pooled effect size of 0.50 (95% CI; 0.17 -0.83),¹⁰⁰ as did an RCT of an ACP workbook that included both behavior 1703 change constructs and a social work visit,¹⁰¹ and our prior RCT of an easy-to-read AD at ZSFG 1704 which showed an increased AD completion rate from 7% to 15%.⁸ Because both the 1705 1706 intervention and control arm will receive the easy-to-read advance directive, we assume that 1707 both arms will have an advance directive completion rate of $\leq 15\%$. Based on prior studies, we 1708 assume PREPARE will result in additional benefit of advance directive completion with a 1709 minimum effect size of 0.5 (two-fold increase) above 15%. A sample of 350, (175 per arm), will 1710 afford us 92% power (2-tailed alpha of 0.05) to detect a difference of advance directive 1711 completion rates of 15% in controls vs. 30% in the PREPARE arm and 80% power to detect a difference of 15% vs. 27%. Power is also expected to be strong for the ACP behavioral change 1712 scale outcomes (preliminary data demonstrated a pre-to-post improvement of 0.5 SD).²⁷ With a 1713 1714 conservative assumption that controls will improve by 0.1 to 0.2 SD, we will have 85% to 98% 1715 power, respectively, to conclude that the improvement is better in the PREPARE arm. We 1716 expect a 15% drop out rate at 12 months based on our prior randomized, controlled trial at ZSFG,⁸ and will therefore attempt to recruit 402 patients, or 201 in each arm for each language 1717 1718 (English and Spanish) for a total recruitment of 804 patients.

1719

Our sample size will also allow adequate power to detect clinically important interactions based on potential moderators (literacy, control preferences, language concordance) for our outcomes. In a prior trial of an easy-to-read advance directive in the same patient population with only 200 patients, we found significant interactions for literacy.⁸ Thus, if we consider the power scenario of the control group ACP documentation rate of 15% and the PREPARE group of 28%, and suppose the control group rate is the same (15%) for both levels of the moderating factor, then

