Human Subjects Protections	May 28, 2014	Because we were assessing depression and anxiety as part of the trial, to err on the side of caution, the Patient-Clinician Stakeholder Advisory Board helped us create a flow diagram with detailed instructions, scripts, and telephone numbers for how staff could refer participants who report severe depression/anxiety if that were to occur. As above, this potential disclosure of participant information was provided on the informed consent form.

2001 Summary of Changes to the Statistical Analysis Plan

Торіс	Date	Summary of Changes
Refusals & withdrawal comparisons	Sep 30, 2016	We added a description of our planned analysis to compare participants who refused based on age and self-reported gender. We also added a description of our planned analysis to compare reasons for withdrawal between study arms.
Bonferroni corrections	Sep 30, 2017	We added Bonferroni adjusted p-values for all secondary and exploratory outcomes.
Stratifying results by language	Mar 1, 2014	Our PCORI grant was funded on Mar 1 st , 2014 and allowed us to add Spanish- speaking participants to the trial. A priori and based on prior literature and the preferences of our stakeholders and grant funders, we added information about stratifying our analysis based on English and Spanish-speaking participants.
Models	Sep 30, 2016	We explain more fully the modeling terms in the mixed effects models.
Variable added to adjusted models	Sep 30, 2016	In addition to health literacy and clustering by clinician, we also adjusted all mixed effects models for baseline ACP documentation because, in consultation with our stakeholders, it was felt that these patients may be different from ACP naïve participants. This also mirrors the analysis in the prior VA PREPARE trial. ³⁵
Effect Size Definitions	Sep 30, 2016	We added information and references concerning clinically meaningful effect sizes.
Exploratory Outcome	Sep 30, 2016	Based on stakeholder request, we included a description of an added exploratory outcome to calculate the percentage of participants who increased their ACP Engagement scores. Bonferroni adjusted p-values for this post-hoc analysis were adjusted to a significance level of 0.017.
Interactions	Sep 30, 2016	We more clearly defined the variables used to test for interactions and how these variables were dichotomized for analysis.

2003 FINAL PROTOCOL REFERENCES

- The United Nations Department of Economic and Social Affairs Population Division.

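### The 85% to 98% power stated for the behavior-change scales predates the Bonferroni adjustment and does not describe the level at which those outcomes will be tested

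*Combined protocol and SAP*

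**What the plan says.** The Statistical Analysis Plan of the final protocol has two-sided p-values, "tailed and set at .05 for the primary outcome and Bonferroni adjusted for secondary" patient-reported outcomes. It names no family and no divisor. The outcomes are introduced with "Secondary outcomes will include ACP Engagement with respect to 5" yes/no actions, a 0-25 action scale and behavior-change scores, at four follow-up visits, and results are to be reported overall and by language. The only numerical Bonferroni level is for the three-part exploratory outcome: "study arm; p-values adjusted to a significance of 0.017".

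The Sample Size section of the final protocol first treats advance directive completion: "A sample of 350, (175 per arm), will" "afford us 92% power (2-tailed alpha of 0.05) to detect a difference of advance directive" completion rates. It then turns to the "scale outcomes (preliminary data demonstrated a pre-to-post improvement of 0.5 SD") and continues: "conservative assumption that controls will improve by 0.1 to 0.2 SD, we will have 85% to 98" percent power. No alpha, sample size or correlation is attached to this second figure. The section expects 15% dropout at 12 months, recruits 201 per arm in each language, works from a single post-intervention time point as the conservative choice, and says longitudinal analyses will be stronger.

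The original protocol gives the same scale power, and its analysis plan contains no Bonferroni adjustment. The log of SAP changes dates the addition to 30 September 2017: "We added Bonferroni adjusted p-values for all secondary and exploratory outcomes".

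**The concern.** The level for these outcomes was tightened and the power was not revisited. A power of 85% to 98% that was already in place before the adjustment cannot describe a test at the adjusted level. The sample is set separately for each language and a language-stratified analysis is planned, so a non-significant engagement result in English or Spanish speakers would be read against a power that is too high for the stated test. Because the divisor is missing, the reader cannot correct the figure, and the significance level for the main patient-reported outcome is not determined by the plan.

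**Working it through.** **Inputs from the final protocol.** PREPARE improves 0.5 SD and controls 0.1 to 0.2 SD, so the between-arm difference is 0.4 to 0.3 SD. Recruitment is 201 per arm per language and dropout is 15%. The SAP is two-sided.

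**Formula.** Two equal arms of n, SD = 1, Bonferroni divisor k:

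power = Φ( d·√(n/2) − z(1 − 0.05/(2k)) )

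**Step 1: the plan's own figure.** Take n = 201, k = 1, critical value 1.960.
- d = 0.3: 0.3 × √100.5 = 3.007; Φ(3.007 − 1.960) = 85.3%.
- d = 0.4: 0.4 × √100.5 = 4.010; Φ(4.010 − 1.960) = 98.0%.

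Both ends match. At k = 1 the same post-only formula gives 80.1% / 96.3% with 175 per arm and 79.2% / 95.9% with 171. The advance directive powers do fit 175 per arm (92.3% and 79.0%).

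The match with 201 is not unique. At 175 per arm and two-sided 0.05, baseline adjustment with an assumed correlation of 0.36 (SD multiplied by √(1 − 0.36²) = 0.933) also gives 85.3% / 98.0%. A change-score test with an assumed correlation of 0.56 gives 84.9% / 97.9%.

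**Step 2: the adjustment alone, whatever the basis.** If 85% and 98% were computed at two-sided 0.05, the standardized effects are 1.960 + 1.036 = 2.996 and 1.960 + 2.054 = 4.014. At divisor 2 the critical value is 2.241, so power becomes Φ(0.755) = 77.5% and Φ(1.773) = 96.2%. This step needs no assumption about n or correlation.

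**Step 3: adjustment and dropout, single time point.** 201 × 0.85 = 171 per arm per language. This is below 175 because 402 is about 350 × 1.15, whereas 350/0.85 = 412. Pooling both languages gives 342 per arm. The divisor is assumed, with a range from 2 (two scores) to 8 (two scores at four visits).

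| Analysis | Divisor | 0.3 SD | 0.4 SD |
|---|---|---|---|
| One language, 171 per arm | 1 | 79.2% | 95.9% |
| One language, 171 per arm | 2 | 70.3% | 92.7% |
| One language, 171 per arm | 3 | 64.8% | 90.4% |
| One language, 171 per arm | 8 | 51.6% | 83.3% |
| Pooled, 342 per arm | 2 | 95.4% | 99.9% |

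For example, at divisor 2 and 0.3 SD: 0.3 × √85.5 = 2.774; Φ(2.774 − 2.241) = 70.3%.

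**Step 4: what baseline information could recover.** At 171 per arm, divisor 2 and 0.3 SD, assumed baseline correlations of 0.5, 0.6 and 0.7 give 83%, 89% and 95% with covariate adjustment (SD × √(1 − r²)). With change scores (SD × √(2(1 − r))) they give 70%, 80% and 91%.

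**Step 5: the pairing.** Controls improving 0.1 SD leaves a 0.4 SD difference, which goes with 98%; 0.2 SD leaves 0.3 SD, which goes with 85%. The text lists 0.1 to 0.2 SD against 85% to 98% *respectively*, which is the reverse.

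**The case against.** The strongest reply is that the calculation above is not the planned test. The SAP fits a mixed model to baseline and four follow-ups, keeps all available data, and so uses participants who leave before 12 months. The power section offers its single-time-point figure as conservative and says the longitudinal analysis will be stronger. With enough within-person correlation, power at divisor 2 returns to the stated range. This stands. The size of the gain cannot be read from the documents, however: no 12-month correlation is given. The nearest figures are intraclass correlations of 0.70 (behavior change) and 0.87 (actions) in the Outcome Measures Table, and the reliability work under Preliminary Studies concerned a 7-day retest.

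The second reply is that the basis of the 85% to 98% is unknown. That also stands. A reader might infer from the match at 201 per arm that dropout was ignored, but the documents do not say so, and Step 1 shows a post-dropout basis that fits equally well.

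A reader might also take 51.6% as the real power. It requires the smaller difference, a divisor of 8, one language and no baseline information, all together.

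Finally, Bonferroni is a valid choice. Replacing it with another procedure, or making some visits or single actions descriptive, would be a design decision that this correction does not need.

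**Conclusion.** The stated scale power does not correspond to the level the SAP now applies. If it was computed at two-sided 0.05, divisor 2 alone lowers it to about 77.5% and 96%. On the single-time-point basis with 171 per arm per language, divisor 2 gives 70.3% and 92.7%, about 15 and 5 points below the stated ends. The shortfall is material only within a language at 0.3 SD: at 0.4 SD power stays above 80% even at divisor 8, and the pooled analysis is well powered at divisor 2.

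A reader might conclude that the trial is underpowered for engagement. The documents do not support that, because the mixed model may recover the loss and its correlation is not stated. The primary outcome, tested at 0.05, is unaffected. The figures rest on a normal approximation, SD = 1, equal arms and an assumed divisor.

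**What to change.** In the Statistical Analysis Plan, state the Bonferroni family and divisor: which scores are tested, whether each contributes one test or one per visit, and whether the overall and language-specific analyses share a family. One example is two tests, Behavior Change and Action, each at alpha 0.025.

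In the Sample Size section, restate the scale power at that alpha with the post-dropout sample. For the example and a single time point this is about 70% when controls improve 0.2 SD and 93% when they improve 0.1 SD within a language, and 95% and above 99% pooled. If repeated-measures power is claimed instead, give the correlation and its source. Correct the pairing so that 0.1 SD goes with the higher power.

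The cost is a few sentences and a less favorable stated power. No change to recruitment, visits or the primary analysis is needed.

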 when they were randomized, they receive a brief reminder call one to 3 days before their
 primary care appointment date. We conduct follow up assessments at 1 week, and at 3, 6,
 and 12 months from this primary care appointment date,
- If they do not reschedule or attend their primary care appointment within 6 months from
 when they were randomized, they receive a brief reminder call one to 3 days before their
 new primary care appointment date. We conduct follow up assessments at 6 and 12 months
 from the originally scheduled primary care appointment date.
- 1529

Ascertaining reasons for loss of follow-up or withdrawal: For participants who want to withdraw, we ask them why in open-ended questions. If they cannot provide an answer, we prompt them from a list of reasons we obtained from prior advance care planning trials, such as the study is too long, they are too busy, the study topic is too upsetting, they are too ill, etc.³⁵

- 1535 **MEASURES**
- 1536 **Overview**

1537 Because ACP ideally is a process that occurs over time, we felt it important to measure a full 1538 range of ACP measures including ACP documentation (primary outcome) over time, and 1539 several behavior change constructs and several additional ACP actions over a 12-month period 1540 (secondary outcomes). All study measures used in this analysis, including validity and reliability 1541 information in English and Spanish and the schedule of administration (i.e., baseline, 1-week or 1542 3, 6, or 12-months), are included in the Outcome Measures table below. All outcomes, including 1543 secondary outcomes not used in our main analysis, are included in our published protocol.³⁶ 1544 The main outcome measures are described in detail below.

1545

1546 **Primary Outcome**

The primary outcome is new documentation of ACP wishes in the ZSFG/SFHN medical record (Table of Outcome Measures below). ACP documentation for the purposes of this study includes the easy-to-read advance directive or other valid advance directives or living wills, a durable power of attorney for health care document (DPOAHC), a Physicians Orders of Life Sustaining Treatment form, or other documentation of discussions concerning patients' wishes for medical care (i.e., documentation of oral directives by a physician or notes describing patients' goals for medical care by clinicians).

1554

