1555 We assess baseline and 15-month new ACP documentation rates and the date of 1556 documentation to determine the length of time from study enrollment to subsequent 1557 documentation. Patients in our study are enrolled, randomized, and exposed to the intervention 1558 1 to 3 weeks prior to a primary care appointment. ACP documentation is timed to the date of 1559 intervention exposure as patients may have engaged in ACP prior to seeing their primary care 1560 provider. The patient-reported outcomes in the follow-up surveys (1 week, 3, 6, and 12-months), 1561 however, are timed to the primary care visit because those questions concern engagement in 1562 discussions with clinicians (see secondary outcomes below). This same timeframe for ACP

- documentation was determined from a prior PREPARE trial conducted within the VA to take into
- account and to standardize the expected time from intervention exposure to the primary care
- 1565 visit and the anticipated time to schedule and complete the final patient interview.³⁵
- 1566

Because legal forms and documented discussions can be used to direct medical care, we created a composite variable of any ACP documentation (forms and/or discussions); we also plan to report the percentage of forms and discussions separately. All medical review data is double coded by 2 independent, blinded research assistants. Discrepancies are adjudicated by the principal investigator ([name]).

1572

1573 Secondary Outcomes

1574 Main Patient-Reported Outcome

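### The primary-outcome model gives new ACP documentation a baseline row and names no tested term; the implied arm-by-time term is not estimable under two codings and inflated under the third

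*Combined protocol and SAP*

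**What the plan says.** All references are to the final protocol.

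- **Measures, Primary Outcome:** "The primary outcome is new documentation of ACP wishes in the ZSFG/SFHN medical record". The same section attaches the word new to both occasions: "We assess baseline and 15-month new ACP documentation rates".
- **Statistical Analysis Plan, comparison:** "Our primary analyses will compare change in ACP documentation between study arms from" baseline to 15 months.
- **Statistical Analysis Plan, model:** mixed effects logistic regression for dichotomous outcomes, with "primary modeling terms of time (baseline and 15 months for ACP documentation", arm, an interaction "term of study arm and time; and a random effect for subjects". Then: "All models also will also be adjusted for baseline ACP documentation and will include random physician intercepts". The Summary of Changes to the Statistical Analysis Plan confirms that this adjustment applies to every mixed model and says it mirrors the earlier VA trial.
- **Statistical Analysis Plan, other covariates:** literacy (the blocking factor), plus any predictors found to differ between the arms.
- **Statistical Analysis Plan, moderators:** "we will test for interactions by adding interaction terms to the group by" time term.
- **Participants and Eligibility:** prior ACP is not an exclusion, so the baseline covariate varies between patients.
- **Sample Size and Power Calculations:** 175 per arm gives 92% power for 15% vs 30% and 80% for 15% vs 27%, at one post-intervention time point. The longitudinal analysis is expected to be stronger.

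No section names the coefficient or contrast that is the primary test, or says what value the baseline row takes for an outcome defined as new.

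**The concern.** An event defined as new since exposure has no natural baseline value, so the analyst must invent one. The plan also enters baseline documentation as a covariate, and under some codings that covariate is identical to the baseline outcome row. The references to change and to the group-by-time term point to arm-by-time as the test, and that is the coefficient that suffers.

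The two-sided .05 for the primary outcome is therefore not tied to a defined estimate. Depending on coding and term, one data set can yield no estimate, an odds ratio of 2.42, or one of 3.31. Under two codings the failure shows when the model is fitted. Under the third it does not: the model converges and looks normal.

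**Working it through.** **1. The plan's own power figures.** Two-proportion formula, pooled variance under the null, n = 175 per arm:

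power = Φ[(p₂ − p₁ − 1.96·√(2p̄(1−p̄)/n)) / √((p₁(1−p₁)+p₂(1−p₂))/n)]

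- 15% vs 30%: (0.15 − 1.96 × 0.04464)/0.04392 = 1.423, power 92.3% (stated 92%).
- 15% vs 27%: (0.12 − 1.96 × 0.04354)/0.04307 = 0.805, power 79.0% (stated 80%).

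Both are reproduced, on a single-row basis. At 350 per arm the formula gives 99.8% and 97.5%.

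**2. Worked example.** 175 per arm; prior documentation assumed at 52/175 in each arm; new documentation 26/175 (control) vs 52/175 (PREPARE). Split by prior status (no, yes), new documentation is 18/123 and 8/52 in controls, and 37/123 and 15/52 in PREPARE. Literacy and clinician terms are left out; the documents give no clustering value.

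*One row per patient.* Crude OR = (52 × 149)/(26 × 123) = 2.42. SE of log OR = √(1/52 + 1/123 + 1/26 + 1/149) = 0.269, so 95% CI 1.43–4.11, p = .001. Adjusting for prior documentation leaves this unchanged.

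*(i) Baseline row 0 for everyone.* The baseline log-odds run to minus infinity in both arms. Arm-by-time is the 15-month difference minus a difference of two infinite quantities, so it is undetermined; the covariate plays no part. Its SE is 10.7, 79, 582 and 4,297 at 8, 12, 16 and 20 iterations (exact values depend on software and starting values). The 15-month contrast, arm plus arm-by-time, is estimable at 2.42. However, each patient has only one informative row, so the subject variance is not identified: fixing the subject SD at 0, 1, 2 or 3 gives ORs of 2.42, 2.79, 3.90 and 5.93, while the log-likelihood changes by 0.0004 and z stays at 3.29–3.33.

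*(ii) Both rows are any documentation on record.* The baseline row equals the covariate, and patients with prior documentation are 1 on both rows. Arm-by-time diverges again (SE 7.8 rising to 3,145). The 15-month contrast rests on the 246 of 350 patients without prior documentation: (37 × 105)/(86 × 18) = 2.51.

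*(iii) Baseline row is prior documentation, 15-month row is new documentation.* This converges. One covariate coefficient must serve a row it predicts perfectly and a row it predicts weakly. Result: OR 3.31 (1.45–7.54), p = .0045, for arm-by-time and also for the 15-month contrast. The likelihood is highest at subject SD 0 (−300.27, against −301.34 at 0.25 and −315.23 at 1), so the random effect does not rescue it.

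**3. Ranges.** Assumed: prior documentation 7–51% and an OR of 1–2 between prior and new documentation. The 7% is the earlier AD completion rate in the sample-size section; the 51% is the VA figure in Preliminary Studies. Each scenario used 10,000 simulated trials and a Wald test.

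| 175 per arm | 15% vs 30% | 15% vs 27% |
|---|---|---|
| Stated power | 92% | 80% |
| One row, power | 92–93% | 79–80% |
| (iii) arm-by-time, power | 47–82% | 34–67% |
| (iii) 15-month contrast, power | 93–95% | 81–85% |
| (ii) 15-month contrast, power | 56–91% | 39–76% |
| One row, limiting OR | 2.43–2.47 | 2.10–2.13 |
| (iii) arm-by-time, limiting OR | 2.83–3.76 | 2.39–2.99 |

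Under the null, the (iii) 15-month contrast rejects 8–13% of the time, arm-by-time 2–9%, and one row 5%.

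At 350 per arm (languages pooled), (iii) arm-by-time has the following power:

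- 15% vs 30%: 78–79% at 7% prior documentation and 92–98% at 15–51% (one row: over 99%).
- 15% vs 27%: 63% and 82–91% (one row: 97–98%).

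The (ii) 15-month contrast has 86–99% and 69–96%. Pooling does not change the limiting odds ratios.

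**4. Which analysis was probably meant.** Preliminary Studies reports 35% vs 25% and OR 1.61 for the VA trial. The simple OR is (0.35/0.65)/(0.25/0.75) = 1.615; coding (iii) would give 1.86–1.96. This suggests a follow-up-only contrast. It is not proof, because the plan does not say how those figures were adjusted.

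**The case against.** The strongest reply is that readers know what is meant. The text points to arm-by-time, and if it fails to converge the analyst will see that and use the 15-month contrast, which under (i) gives the same test as one row per patient. The inflated odds ratio belongs to (iii), a coding the plan never states and that the VA figures argue against. Its size rests on assumed inputs, and the lowest power figures use an AD-only rate for a composite that also counts documented discussions.

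Much of this is fair. Coding (iii) is a possible reading, not a stated one. Its inflation is also not universal: it is small at 5% prior documentation (2.63–2.88 against 2.43–2.48 across prior/new ORs of 0.1–4). At a prior/new OR of 0.25 it persists (2.71–2.92 against 2.45–2.60 at 7–51% prior). It reverses in an extreme corner, OR 0.1 with 51% prior (2.68 against 2.86). Pooling largely removes the shortfall against the stated power.

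The point survives for three reasons. Non-estimability under (i) and (ii) needs no assumption about prevalence. Coding (iii) is the only one of the three under which the implied term can be fitted, so an analyst facing divergence may arrive there. And naming the 15-month contrast while keeping two rows settles the test under (i) but not the odds ratio, which then depends on a subject variance the data cannot estimate.

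**Conclusion.** The concern holds: the primary model is wrong as written and should be fixed. Under each of the three codings that fit the text, the implied test either cannot be computed or can misstate the effect. The non-estimability is structural. The inflation (about 2.8–3.8 instead of 2.4 for 15% vs 30%) and the power loss apply only to coding (iii), given 7–51% prior documentation and a prior/new OR of 1–2. Under the null the typical odds ratio in (iii) stays near 1, so what is distorted is effect size, test level and power.

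The expectation that the longitudinal analysis will be stronger than a single time point does not hold for arm-by-time on this outcome: under (iii) it was weaker than one row per patient in every scenario run. Separately, adjusting for predictors found to differ between arms leaves the primary model's covariates to be chosen after the data are seen.

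**What to change.** For the primary outcome, specify one row per patient: a logistic model of new ACP documentation by 15 months (yes/no) on arm, baseline ACP documentation and the literacy stratum used for blocking, with a random clinician intercept. Name the arm coefficient as the primary test at two-sided .05.

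- Drop time, arm-by-time and the subject random effect for this outcome.
- Test moderators of this outcome as arm-by-moderator terms in the same model.
- Remove the data-driven covariate clause from the primary model.
- Keep the longitudinal mixed model for the engagement scores.

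This agrees with the single-time-point power calculation and, in the simulations, kept the planned power and a 5% null rejection rate. The cost is SAP wording only, since all the variables are already collected. Because the final protocol is dated September 2017, the change should be dated and its timing relative to access to outcome data by arm recorded.
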